10.5.2. Time to Progression (TTP)

TTP is defined as the time from the first dose date (i.e. the first dose of CC-122 or Nivolumab whichever occurred first) until tumor progression; TTP does not include death. The censoring rules for TTP are the same as described for PFS, except deaths without progression are censored at the time of the date of last adequate tumor assessment.

For TTP by RECIST 1.1, a subject who has not progressed will be censored on the date of last adequate tumor assessment. Subjects without valid baseline or post-baseline tumor assessments will be censored on their first dose dates. Any valid overall post-baseline tumor assessment (not recorded as “not done” or “not all evaluable”) are considered adequate tumor assessments in this case.

For TTP by irRECIST, the date of progression is the first date of PD as defined under irRECIST. A subject who has not progressed or who progresses or dies after an extended lost-to-follow up time (two or more missed assessments) will be censored on the date of his or her last adequate tumor assessment. Subjects without valid baseline or post-baseline tumor assessments will be censored on their first dose dates (i.e. the first dose of CC-122 or Nivolumab whichever occurred first).

Analysis of TTP will be provided for RECIST and irRECIST separately and presented for the Safety and EE Populations. Median of TTP will be calculated using the Kaplan-Meier method and the corresponding 95% CIs will be presented.

11. SAFETY ANALYSIS

The purpose of this section is to define the safety parameters for the study and to summarize the safety result of the study. All summaries of safety data will be conducted using the Safety Population and will be presented by dose cohorts in the dose escalation part by selected subgroups in the dose expansion part, and by selected subgroup at the expanded dose with subjects from both parts. Safety measurements will include AEs, clinical laboratory information (including troponin-T and Brain natriuretic peptide [BNP]), vital sign measurements, 12-lead electrocardiograms (ECGs), left ventricular ejection fraction (LVEF) assessments, ophthalmological exam, and pregnancy status. Individual subject listings will be provided to support the tables.

If an EOT measurement is conducted for those subjects who discontinue from the study, the data from the EOT visit will be included as a separate visit in the summary table. In addition, the data from the EOT visit will also be included in plots for parameters of individual subjects over time.

11.1. Adverse Events

11.1.1. Summary of Adverse Events

AEs will be analyzed in terms of treatment-emergent adverse events (TEAEs) which are defined as any AEs that start between the date of first dose of study drug and 28 days after the last dose of CC-122 or 90 days after the last dose of Nivolumab, whichever is later. All AEs will be coded using the MedDRA[®] dictionary Version 21.0 or higher.

The incidence of TEAEs will be summarized by MedDRA SOC and PT. The intensity of AEs will be graded 1 to 5 according to the National Cancer Institute (NCI) Common Terminology Criteria for Adverse Events (NCI CTCAE) Version 4.03 or higher if possible. AEs that are not defined in the NCI CTCAE Version 4.03 or higher should be evaluated for severity/intensity according to Version 3.0. For all other AEs not described in the NCI CTCAE criteria, the intensity will be assessed by the investigator as mild (grade 1), moderate (grade 2), severe (grade 3), life-threatening (grade 4) or death (grade 5).

If a subject experiences the same AE more than once with a different grade, then the event with the highest grade will be tabulated in “by grade” tables. If a subject experiences multiple AEs under the PT (SOC), then the subject will be counted only once for that PT (SOC). In addition, AEs with a missing grade will be presented in the summary table as a grade category of “Missing” and will not be imputed.

A summary table of the subject incidence rate in each of the following categories will be provided. In addition, a table for each of the following categories will be produced where the incidence rate will be tabulated by SOC and PT and provided.

- TEAEs;
- TEAEs related to CC-122, Nivolumab and study drugs (CC-122 and/or Nivolumab);
- TEAEs of NCI CTCAE grade 3 or 4 by maximum NCI CTCAE grade;

- TEAEs related to CC-122, Nivolumab and study drugs (CC-122 and/or Nivolumab) with NCI CTCAE grade 3 or 4 by maximum NCI CTCAE grade;
- Grade 5 TEAEs with death outcome;
- Grade 5 TEAEs with death outcome related to CC-122, Nivolumab and study drugs (CC-122 and/or Nivolumab);
- Serious TEAEs;
- Serious TEAEs related to CC-122, Nivolumab and study drugs (CC-122 and/or Nivolumab);
- TEAEs leading to discontinuation of CC-122, Nivolumab and both study drugs (CC-122 and Nivolumab);
- TEAEs related to CC-122 leading to discontinuation of CC-122 and both study drugs (CC-122 and Nivolumab);
- TEAEs related to Nivolumab leading to discontinuation of Nivolumab and both study drugs (CC-122 and Nivolumab);
- TEAEs related to study drugs (CC-122 and/or Nivolumab) leading to discontinuation of CC-122, Nivolumab, and both study drugs (CC-122 and Nivolumab);
- TEAEs leading to dose reduction of CC-122;
- TEAEs related to CC-122 leading to dose reduction of CC-122;
- TEAEs related to study drugs (CC-122 and/or Nivolumab) leading to dose reduction of CC-122;
- TEAEs leading to dose interruption of CC-122, Nivolumab and both study drugs (CC-122 and Nivolumab);
- TEAEs related to CC-122 leading to dose interruption of CC-122 and both study drugs (CC-122 and Nivolumab);
- TEAEs related to Nivolumab leading to dose interruption of Nivolumab and both study drugs (CC-122 and Nivolumab);
- TEAEs related to study drugs (CC-122 and/or Nivolumab) leading to dose interruption of CC-122, Nivolumab and both study drugs (CC-122 and Nivolumab);

As well as

- TEAEs by cycle of onset;
- TEAEs related to CC-122, Nivolumab and study drugs (CC-122 and/or Nivolumab) by cycle of onset;
- TEAEs by maximum NCI CTCAE grade;
- TEAEs related to CC-122, Nivolumab and study drugs (CC-122 and/or Nivolumab) by maximum NCI CTCAE grade;
- Common ($\geq 10\%$) TEAEs;

- Common ($\geq 10\%$) TEAEs related to CC-122, Nivolumab and study drugs (CC-122 and/or Nivolumab);
- The selected TEAEs of interest

Selected TEAEs/ serious AEs (SAEs) of interest as determined by the mechanism of action, known class effects, or TEAEs observed to date will be summarized by cohort and grade or as needed. Standardized MedDRA queries (SMQs) will be used in the search strategy for some of the selected AEs of interest, intending to aid in case identification. The groupings of selected AEs, described by one phrase or topic term will be determined by clinicians based on SMQ or relevant search terms and provided to the statistical team, prior to database lock. To facilitate clinical study report (CSR) writing, a summary table of selected TEAEs of interest by PTs will also be provided.

The following tabulated lists will be provided together with AE tables,

- List of subjects who died by phase, dose cohort/disease subtype, subject number, SOC, and PT.
- List of SAEs by phase, dose cohort/disease subtype, subject number, SOC and PT;
- List of TEAEs leading to permanent withdrawal of study drug by phase, dose cohort/disease subtype, subject number, SOC, and PT;

Individual subject listings of AEs and AESIs will be presented. In addition, following tabulated lists will be provided as well,

- List of TEAEs that fulfill any of the DLT (see section 11.1.2) criteria by phase, dose cohort, subject number, DLT term, SOC, and PT
- List of TEAEs with NCI CTCAE grade 3 or 4 by phase, dose cohort/disease subtype, subject number, SOC, and PT
- List of TEAEs leading to dose reduction and dose interruption of study drug by phase, dose cohort/disease subtype, subject number, SOC, and PT.

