10.2.1.	Seriousness	80
10.2.2.	Severity / Intensity.....	82
10.2.3.	Causality	82
10.2.4.	Duration	83
10.2.5.	Action Taken	83
10.2.6.	Outcome.....	83
10.3.	Abnormal Laboratory Values.....	83
10.4.	Pregnancy.....	83
10.4.1.	Females of Childbearing Potential	84
10.4.2.	Male Subjects	84
10.5.	Reporting of Serious Adverse Events.....	85
10.5.1.	Safety Queries	85
10.6.	Expedited Reporting of Adverse Events.....	85
11.	DISCONTINUATIONS	87
11.1.	Treatment Discontinuation.....	87
11.2.	Study Discontinuation	87
12.	EMERGENCY PROCEDURES	88
		
12.2.	Emergency Identification of Investigational Products	88
13.	REGULATORY CONSIDERATIONS.....	89
13.1.	Good Clinical Practice	89
13.2.	Investigator Responsibilities	89
13.3.	Subject Information and Informed Consent.....	90
13.4.	Confidentiality.....	90
13.5.	Protocol Amendments.....	90

LIST OF TABLES

Table 1:	Study Objectives.....	32
Table 2:	Study Endpoints	33
Table 3:	Table of Events.....	42
Table 4:	Dose Levels.....	57
Table 5:	Allowed Dose Reductions.....	61
Table 6:	Dose Adjustment Guidelines for CC-122 Related Non-hematologic Toxicities.....	62
Table 7:	Dose Adjustment Guidelines for CC-122 Related Hematologic Toxicities	65
Table 8:	Recommended Treatment Modification for Nivolumab	66
Table 9:	Confidence Interval for 20% and 35% Response Rate for Different Scenarios of Sample Size (Wilson Score Interval)	76
Table 10:	Abbreviations and Specialist Terms	101
Table 11:	Time Point Response: Subjects With Target (\pm Non-target) Disease	108
Table 12:	Time Point Response: Subjects With Non-target Disease Only	109
Table 13:	Child-Pugh Classification	119

LIST OF FIGURES

Figure 1:	Effect of CC-122 Combined with Nivolumab on IL-2 Secretion from SEB Stimulated PBMC.....	23
Figure 2:	Effects of CC-122 and Nivolumab in PBMC-mediated-Killing of JHH4 Cells	24
Figure 3:	Overall Study Design.....	36
		
Figure 5:	BCLC Staging and Treatment Schedule	118
Figure 6:	Diarrhea Management Guidelines	137

Table 2: Study Endpoints

Endpoint	Name	Description	Timeframe
Primary Phase 1	The incidence of dose limiting toxicities (DLTs) and the incidence and severity of treatment-emergent adverse events (TEAEs)	See Section 7.6 for the definition of DLTs	End of Phase 1
Primary Phase 2	Preliminary efficacy as measured by overall response rate (ORR)	The combined incidence of complete response (CR) + partial response (PR), by investigator assessment of response by Response Evaluation Criteria in Solid Tumors (RECIST) 1.1	End of Study

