9.7. Safety Analysis

All summaries of safety data will be conducted using subjects receiving at least one dose of either IP (the Treated Population).

Adverse events observed will be classified using the Medical Dictionary for Regulatory Activities (MedDRA). The severity of the toxicities will be graded according to the NCI CTCAE (Version 4.03) whenever possible. The frequencies of adverse events will be tabulated by MedDRA (Version 17.1 or higher) SOC and PT. In the by-subject analysis, a subject having the same AE more than once will be counted only once. Adverse events will also be summarized by NCI CTCAE grade. Investigational product-related AEs, AEs leading to dose reduction/interruption, or permanent discontinuation of study treatment, events classified as CTCAE Grade 3 or 4, deaths, and SAEs will be tabulated. By-subject listings of all AEs, deaths, serious AEs (SAEs) and their attribution will be provided.

Clinical laboratory results will be summarized descriptively, which will include a display of change from baseline. Bidirectional shift tables (low and high) demonstrating the change of CTCAE grades from baseline to the worst post-baseline severity grade during the treatment period will also be presented for applicable tests. Listings of abnormal clinical laboratory data according to NCI CTCAE severity grades (if applicable), abnormal flags (low or high) will be provided. Graphical displays (eg, "spaghetti" plots or box plots) will be provided for key laboratory tests.

Descriptive statistics for ECG, vital sign and LVEF measurement, both observed values and changes from baseline, will be summarized. Shift tables demonstrating the changes from baseline to the worst post-baseline qualitative assessment of abnormality will be displayed in cross-tabulations. Post-baseline abnormal ECG and LVEF values will be summarized using frequency tabulations. Electrocardiogram, vital sign and LVEF measurements will be listed by subject. Graphical displays will be provided where useful to assist the interpretation of results.

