All AEs will be recorded by the Investigator from the time the subject signs informed consent until 28 days after the last dose of CC-122 and until 90 days after the last dose of nivolumab and those SAEs made known to the investigator at any time thereafter that are suspected of being related to CC-122 or nivolumab. Adverse events and SAEs will be recorded on the AE page of the eCRF and in the subject's source documents. All SAEs must be reported to Celgene Drug Safety within 24 hours of the Investigator's knowledge of the event by facsimile, or other appropriate method, using the SAE Report Form, or approved equivalent form.

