10.5. Reporting of Serious Adverse Events

Any AE that meets any criterion for an SAE requires the completion of an SAE Report Form in addition to being recorded on the AE page/screen of the eCRF. All SAEs must be reported to Celgene Drug Safety within 24 hours of the Investigator's knowledge of the event by facsimile, or other appropriate method, using the SAE Report Form, or approved equivalent form. This instruction pertains to initial SAE reports as well as any follow-up reports.

The Investigator is required to ensure that the data on these forms is accurate and consistent. This requirement applies to all SAEs (regardless of relationship to CC-122 or nivolumab) that occur during the study (from the time the subject signs informed consent until 28 days after the last dose of CC-122 or until 90 days after the last dose of nivolumab) or any SAE made known to the Investigator at any time thereafter that are suspected of being related to either IP. Serious adverse events occurring prior to treatment (after signing the ICF) will be captured.

The SAE report should provide a detailed description of the SAE and include a concise summary of hospital records and other relevant documents. If a subject died and an autopsy has been performed, copies of the autopsy report and death certificate are to be sent to Celgene Drug Safety as soon as these become available. Any follow-up data should be detailed in a subsequent SAE Report Form, or approved equivalent form, and sent to Celgene Drug Safety.

Where required by local legislation, the Investigator is responsible for informing the Institutional Review Board (IRB) /Ethics Committee (EC) of the SAE and providing them with all relevant initial and follow-up information about the event. The Investigator must keep copies of all SAE information on file including correspondence with Celgene and the IRB/EC.

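### SAP 11.1.1 counts related, serious and Grade 5 events only if they start in the TEAE window, so no planned incidence summary includes the late suspected-related SAEs that the protocol keeps collecting

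*SAP*

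**What the plan says.** **Analysis window.** SAP 11.1.1 analyses adverse events as TEAEs. To qualify, an event must start once dosing has begun and before a fixed cut-off: "28 days after the last dose of CC-122 or 90 days after the last dose of Nivolumab, whichever is later".

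**Incidence categories.** The same section plans a subject-incidence summary, and SOC/PT tables, for a list of categories. Those that matter here are all TEAEs, related TEAEs, serious TEAEs, "Serious TEAEs related to CC-122, Nivolumab and study drugs (CC-122 and/or Nivolumab"), Grade 5 TEAEs, and "Grade 5 TEAEs with death outcome related to CC-122, Nivolumab and study drugs (CC-122 and/or Nivolumab"). None adds events that start after the window.

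**Collection.** Protocol 10.1 records all AEs to the end of the same 28-day and 90-day periods, and after that "those SAEs made known to the investigator at any time thereafter that are suspected of being related to CC-122 or nivolumab". Protocol 10.5 repeats the rule for SAE reporting: "any SAE made known to the Investigator at any time thereafter that are suspected of being related to either IP". The tables of events (protocol Table 3, SAP Table 14) also leave collection open-ended for events judged related, without limiting this to serious ones.

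**Promised reporting.** Protocol 9.7 lists IP-related AEs among the items to be tabulated, and the same sentence ends with "events classified as CTCAE Grade 3 or 4, deaths, and SAEs will be tabulated". It names no onset window. A separate sentence covers listings: "By-subject listings of all AEs, deaths, serious AEs (SAEs) and their attribution will be provided".

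**Lists in the SAP.** SAP 11.1.1 plans tabulated lists of SAEs and of subjects who died, neither restricted to TEAEs, as well as individual AE listings. The keys named for the two lists are phase, dose cohort or disease subtype, subject number, SOC and PT.

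**The concern.** After the window closes, the only events that protocol 10.1 still requires are SAEs suspected of being caused by one of the study drugs. Those are the events that the related, serious related and Grade 5 related rates leave out. The sponsor would hold the data, and the protocol announces tabulation without a window, yet no planned number or percentage of subjects would reflect them.

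This bears on how the combination's safety is read. Safety and tolerability is the Phase 1 primary objective. SAP section 15 (item 2) says the study will not enter expansion, so the small escalation cohorts supply the safety data, and SAP 11 reports them by dose cohort. Someone who takes the serious related rate as the summary of drug-attributed harm would have to know to look for late events in separate lists. Attribution is not a named key of the SAE or death list.

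**Working it through.** There is no planned figure to reproduce. The check compares the texts and adds one illustration.

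**Step 1: which events fall between the rules?**

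| Event | Collected? | In a SAP 11.1.1 incidence category? | In SAP lists or listings? |
|---|---|---|---|
| Related SAE starting in the window | Yes (10.1) | Yes | Yes |
| Event starting in the window, later serious or fatal | Yes | Yes, because the rule uses start date | Yes |
| AE with wholly missing start date | Yes | Yes (SAP 17.4.1 counts it as a TEAE) | Yes |
| Suspected-related SAE starting after the window | Yes (10.1, 10.5) | **No** | Yes: SAE list, AE listings, death list if fatal |

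Only the last row is affected. The planned summary of selected TEAEs and SAEs of interest might take in some of these events, since its wording is ambiguous. It is organised by topic and is not a related, serious or Grade 5 rate.

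**Step 2: is the limit declared?** The visible items of SAP section 15 record changes as small as an added AESI listing and an overdose count. None says that related AEs, SAEs or deaths are limited to the TEAE window.

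**Step 3: how far could a rate move?** The number of late events is not in the documents. Assume one subject whose only event in the category starts late. The rate is x/n, with x = 0 under the SAP rule and x = 1 with the late event counted. The 95% limits are Clopper-Pearson. For x = 0 the upper limit is 1 − 0.025^(1/n), and for x = 1 the lower limit is 1 − 0.975^(1/n).

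Denominators: 3 (protocol 7.8 allows escalation after three evaluable subjects), 6 (full cohort, protocol 7.8) and 20 (approximate escalation maximum, protocol 9.3).

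| n | SAP rule | Late event counted |
|---|---|---|
| 3 | 0/3 = 0% (0 to 70.8) | 1/3 = 33.3% (0.8 to 90.6) |
| 6 | 0/6 = 0% (0 to 45.9) | 1/6 = 16.7% (0.4 to 64.1) |
| 20 | 0/20 = 0% (0 to 16.8) | 1/20 = 5.0% (0.1 to 24.9) |

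At 30 subjects, the upper estimate in protocol 7.2.1, the change is from 0% to 1/30 = 3.3%. The intervals overlap widely, so precision is not the issue. What changes is whether the event shows in the rate at all. If the subject already has an in-window event in the category, that rate does not move.

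**Step 4: where must late events be added?** If they were added to the related rows only, a cohort of six could show 1/6 serious related beside 0/6 serious, a subset larger than its parent. Let S be the subjects with a serious TEAE, R the subset with a related one, and L the subjects with a late suspected-related SAE. Adding L to both keeps R ∪ L inside S ∪ L. The same holds for the Grade 5 pair and the any-TEAE pair, so the all-cause lines need the companion row too.

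**The case against.** The strongest case is that this is a matter of presentation.

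- **The window is principled.** It ends where full AE collection ends, and the Phase 1 primary endpoint is worded as "the incidence and severity of treatment-emergent adverse events (TEAEs"). After it, only SAEs that reach the investigator and are suspected of being related are captured, so ascertainment is passive and selective. Keeping such events out of the main rates is defensible. This stands, and the TEAE definition should not change.
- **The lists may satisfy protocol 9.7.** The SAP calls its SAE and death lists tabulated and does not restrict them to TEAEs. For all-cause SAEs and deaths this has force. It is weaker for IP-related AEs: no tabulated list of related AEs is planned, and lists give no incidence. Protocol 9.7 does ask for attribution in the by-subject listings, and nothing visible in the SAP withdraws that. With about 20 subjects, a careful reader could therefore count late related events by hand.
- **The effect is hypothetical, and unlikely for the broadest category.** The protocol's amendment justification reports rash with resulting DLTs during escalation, and protocol 7.10.4.1 cites neutropenia in about 50% of subjects in part of another CC-122 study. Most subjects may well have an in-window related event, so the any-related rate would rarely move. The serious related and Grade 5 related rates are the ones that could.

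A reader might infer that late related SAEs go unreported. The documents do not support that, because they appear in the lists and listings. Nor do they support reading the TEAE window as an error or a breach of the primary endpoint.

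**Conclusion.** The point holds as a small gap between what is collected and what is summarised. Followed as written, the SAP leaves a known suspected-related SAE that starts after the window out of every related, serious and Grade 5 incidence category, although protocol 9.7 promises tabulation without that limit.

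Its size depends on a count that the documents do not give: nothing if no such event occurs, and for one subject with no other event in the category, 33 points in a cohort of 3, 17 points in a cohort of 6 and 5 points over 20. Severity is low.

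A reader might also suppose that dose finding is affected. It is not: DLTs are confined to Cycle 1 (with the predose assessments of Cycle 2 Day 1), and the TEAE-based primary endpoint is reported as defined. Redacted SAP text was not treated as missing. The conclusion rests on the visible text of SAP 11.1.1 and section 15.

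**What to change.** Keep every window-only TEAE rate as planned. Add to SAP 11.1.1:

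> In the overall summary of adverse events, the rows for TEAEs, related TEAEs, serious TEAEs, serious related TEAEs, Grade 5 TEAEs and related Grade 5 TEAEs will each be followed by a separately labelled companion row, by dose cohort. It gives the number and percentage of subjects when SAEs that start after the TEAE window and are suspected of being related to CC-122 or Nivolumab are included. A footnote will state that events after the window are passively ascertained.

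Also add attribution to each drug as a key of the SAE and death lists, and record both changes in SAP section 15.

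The cost is a short paragraph, one derivation flag, six rows in one summary table and one extra column in two lists. No new data are needed. The downside is that the companion rows are incompletely ascertained and may look slightly less favourable. The window-only rates beside them keep the primary endpoint unchanged, and if no late event occurs the paired rows are identical.
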